1 OBJECTIVES

- To investigate objectively using evidence based randomized controlled trial the impact of early mobility (first day after the surgery) after any inpatient oncologic procedures on early recovery of postoperative course.
- Try to find out the minimum level of postoperative mobility that needed for early postoperative course recovery by objective assessment of range of movement for each participant using 3D motion tracking system (Xsens)

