3 INCLUSION AND EXCLUSION CRITERIA

Inclusion Criteria

To be included in this study, participants must meet the following criteria:

1. Age \geq 18 years of age.
2. Ambulant inpatient with a stay of \geq 2 days after any oncologic surgery.
3. ECOG scale of performance status of less than 3.
4. American Society of Anesthesiologist score (ASA) 3 or less

PROTOCOL TITLE: Does increased mobility assessed with 3D motion tracking technology lead to early post-operative recovery among patients undergoing oncologic surgeries

5. Participants who do not engage in regular exercise regimen before the surgery (other than regular occupational physical therapy).
6. Participant or legal representative must understand the investigational nature of this study and sign an Independent Ethics Committee/Institutional Review Board approved written informed consent form prior to receiving any study related procedure.

Exclusion Criteria

Patients with altered mental status, psychiatric illness, ECOG scale performance status 3 or more, ASA score of 4, participants who engage in regular exercise regimen before surgery (at least one session per week), restricted movement due to other diseases or those who require continuous monitoring will be excluded from this study.

Inclusion of Women and Minorities

Women and members of all races and ethnic groups are eligible for this study. Pregnant women are eligible for this study.

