8 STUDY ENDPOINTS

The primary study endpoint is measuring early recovery of postoperative course by calculating early return of bowel motion (passing flatus and/or stool on which postoperative day), presence or absence of nausea and/or vomiting, presence or absence of chest symptoms (cough, sputum

PROTOCOL TITLE: Does increased mobility assessed with 3D motion tracking technology lead to early post-operative recovery among patients undergoing oncologic surgeries

and ability of using incentive spirometry), early discharge from the hospital and 30 days surgical related complications and readmissions.

The secondary study endpoint is measuring the range of joint movement in upper and lower joints of body, using the 3D motion tracking system (Xsens), to identify the minimum required level of mobility for better early postoperative course recovery.

A few other secondary endpoints concluded from the post experiment questionnaire include: assessing encouraged walking in the hospital setting subjectively improves their exercise habit outside of the hospital, how was the application of the sensors in a hospital setting as this is the first study to do so, and to assess the subjective impact of complications on quality of life.

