9 PROCEDURES INVOLVED

This is a prospective randomized controlled trial comparing the early postoperative course of patients who undergo inpatient oncological procedures after assessment of their baseline physical activity before the surgery, using validated questionnaires in the clinic, to have a homogenized sample for the study. Participants will be randomized to the control arm (40 participants) and intervention group (40 participants). Control group participants will be asked to walk one to two laps around the ward twice per day, on the first day after the surgery following the usual clinical practice at Roswell Park Comprehensive Cancer Center-urology department (RPCCC). Their movement will be tracked with 3D motion tracking system (Xsens). The intervention arm participants will be asked to walk for minimum 30 minutes per day and their movement also will be tracked with Xsens. In both arms the patients will be asked to mobilize (walk out of the bed) on first day post-surgery under supervision and assistant of attending nurse in the floor if their clinical situation allowed. If patient cannot complete the walking tasks, they will be excluded from the study and they will be replaced by recruiting other patients.

Xsens is a wireless technology that makes use of sensors. The sensors are applied in a non-invasive manner and do not require the suit to be applied. There are various configurations of the sensors that can be utilized. The minimum number of sensors needed is 7. They are applied by using Velcro bands. The entire set-up takes about 5-10 minutes.

The study duration is 24 months or until target accrual is reached. In both arms their mobility will be tracked till they discharged from the hospital. In both arms we will assess the symptoms and signs of gastro-intestinal complications (nausea, vomiting, abdominal pain, passing flatus or stool) and chest symptoms (coughing, sputum, utilizing incentive spirometry) until they are discharged from the hospital. We will continue to follow them for 30 days post discharge to note any complications or readmission.

Patients at standard follow ups, 2 weeks, 6 weeks, 3 months or over the phone will complete a short post study questionnaire (Appendix B). The last three questions are taken from Woodfield et al., who assessed postoperative problems from the perspective of the patient on the identification of complications after surgery (11).

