16 STATISTICAL PLAN

Demographics: Subject demographic and clinical characteristics will be reported by group using the appropriate descriptive statistics and graphical summaries. Comparisons will be made between groups using the Mann-Whitney U or Chi-square tests, as appropriate.

Randomization: Subjects will be randomized to the control and intervention groups in a 1:1 fashion using a permutation block design (block sizes = 4). The randomization list will be developed by the study statistician.

Primary Analysis: The primary objective is to evaluate changes in mobility between the control (standard of care) and intervention (additional activity) groups. The primary outcomes are measures of mobility (i.e. range of movement), which are treated as continuous measures and will be summarized by group and time-point using the mean, median, and standard deviation. The measures of mobility will each be modeled as a function of treatment group, time post-surgery, their two-way interaction, and random subject effects using a linear mixed model. Within each group, the effect of time on the mean will be evaluated using tests about the appropriate contrasts of model estimates. The effect of the two groups on the time-mobility relationship will be evaluated using an F-test about the interaction term. All model assumptions will be evaluated graphically and transformations will be applied as necessary.

Secondary Analyses: The secondary objective is to evaluate the impact on post-surgical complications. The complication status (present/absent) and grades will be summarized by group and compared using Fisher's exact test or the chi-square test, as appropriate.

PROTOCOL TITLE: Does increased mobility assessed with 3D motion tracking technology lead to early post-operative recovery among patients undergoing oncologic surgeries

The association between complication status and changes in measures of mobility may be evaluated using logistic regression models.

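### Objective 2 asks what mobility level is needed for recovery, but achieved mobility is not randomised and no analysis adjusts for fitness or extent of surgery

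*Combined protocol and SAP*

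**What the plan says.** Section 1, second objective: to try to find the "minimum level of postoperative mobility that needed for early postoperative course recovery", judged from each participant's measured range of movement. Section 8 gives the same aim as a secondary endpoint, measured with the motion sensors: "to identify the minimum required level of mobility for better early postoperative course recovery".

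Section 9 defines what is randomised. In one arm, "Control group participants will be asked to walk one to two laps around the ward twice per day"; in the other, "The intervention arm participants will be asked to walk for minimum 30 minutes per day". Walking on the first day is conditional on the patient's clinical situation, and patients who cannot complete the walking tasks are excluded and replaced. Section 16 describes the allocation: "Subjects will be randomized to the control and intervention groups in a 1:1 fashion using a permutation block design (block sizes = 4"). It states no stratification.

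Section 16 contains one sentence that relates measured mobility to an outcome: "The association between complication status and changes in measures of mobility may be evaluated using logistic regression models". It names no covariates. Section 16 describes no method for finding a minimum level, and nothing labels the aim as exploratory.

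Section 3 admits an "ECOG scale of performance status of less than 3", an ASA score of 3 or less, and any oncologic surgery with a stay of at least two days.

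**The concern.** The words *needed* and *minimum required* say that reaching a certain level brings recovery about. Randomisation can support a causal statement about the instruction to walk more. It cannot support one about the level reached, because patients sort themselves into levels after randomisation. A fitter patient, or one who had a smaller operation, may both move more and recover sooner. Comparing patients by achieved mobility would then show a gradient, and a cut-point on it, with no contribution from movement.

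This comes from the design, not from the choice of model. It would remain if the Section 16 model were made mandatory, extended to the recovery endpoints and given the right time order. What is at stake is a published mobility target that marks who was fitter but is read as a level that patients must reach.

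**Working it through.** **The plan's own figure.** Section 16 states 80% power for 0.63 SD with 40 per group, two-sided alpha 0.05. Detectable difference = (1.960 + 0.842) × √(2/40) = 2.802 × 0.2236 = 0.627 SD (0.634 SD with the noncentral t). The figure reproduces. It concerns the difference in mobility between arms and says nothing about the link from mobility to recovery.

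**Inputs.** From the documents: n = 80 (two arms of 40) and alpha 0.05 two-sided. Assumed, because the documents give no value: one fitness factor correlating r with mobility and r with recovery, r from 0.3 to 0.6; no effect of mobility or arm on recovery; 30% events for a binary outcome.

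**Mobility level against a continuous recovery measure.** Fitness alone induces a correlation ρ = r × r. By the Fisher transformation, the chance of p < 0.05 is Φ(d − 1.96) + Φ(−d − 1.96), with d = atanh(ρ) × √(80 − 3). For r = 0.5: ρ = 0.25, d = 0.2554 × 8.775 = 2.241, so Φ(0.281) = 61%.

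**Mobility level against a binary outcome.** Cutting recovery at 30% events multiplies ρ by φ(0.524)/√(0.3 × 0.7) = 0.348/0.458 = 0.759. For r = 0.5: ρ = 0.190, d = 0.192 × 8.775 = 1.685, so Φ(−0.275) = 39%.

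| r | ρ | Continuous: formula (simulated) | Binary: formula (simulated) |
|---|---|---|---|
| 0.3 | 0.09 | 12% (12%) | 9% (9%) |
| 0.4 | 0.16 | 29% (30%) | 19% (19%) |
| 0.5 | 0.25 | 61% (61%) | 39% (38%) |
| 0.6 | 0.36 | 91% (92%) | 69% (71%) |

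On the continuous scale, the more mobile half recovers about 0.25 SD sooner at r = 0.4 and about 0.39 SD sooner at r = 0.5, with no true effect. If the arms differ by 0.63 SD in mobility, the continuous rates fall only slightly: 27% at r = 0.4 and 58% at r = 0.5.

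**Change in mobility, as in the Section 16 model.** Write baseline = rF + e₁ and discharge = rF + e₂, where F is fitness. Change = e₂ − e₁. F cancels, and the false-positive rate is about 5% at every r tried. With unequal loadings r_b and r_d, the covariance of change with recovery is (r_d − r_b) × r, and the bias returns. Extent of surgery need not cancel: if baseline is taken before the operation, it acts only on the later measurement. Section 9 does not say when baseline mobility is measured.

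**What adjustment achieves.** For a covariate correlating 0.7 with fitness, the partial correlation is 0.51ρ/(1 − 0.49ρ). At r = 0.5 this is 0.1275/0.8775 = 0.145, so d = 0.146 × √76 = 1.28 and the rate is 25% (unadjusted 61%). Over r = 0.3 to 0.6 the adjusted rate is 7% to 51%. Adjustment helps but does not remove the bias.

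**Adding arm.** At r = 0.5, logistic regression on achieved mobility gave 38–40% without arm and 40–43% with it (event rates 30% and 50%). Arm takes out the only randomised part of the variation in mobility and leaves the confounded part.

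**Comparison by randomised arm.** The false-positive rate stayed at 4–6% throughout, with all simulated patients kept.

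**The case against.** The strongest reply has four parts.

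*No threshold analysis is written.* This is correct. Section 1 speaks only of trying to find the level, and the one relevant model in Section 16 is optional and already speaks of association. A reader might infer that the plan commits to publishing an unadjusted minimum level; the documents do not support that. The aim is nevertheless stated twice in causal words, and any analysis that meets it from these data must compare patients by achieved mobility.

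*The large percentages do not describe the Section 16 model.* This is also correct. A reader might apply the 12% to 92% range to it. That range is for mobility level against a continuous outcome, whereas Section 16 models a binary complication status on change, where the rate may be near 5%. Sections 1 and 8, however, ask about a level, not a change.

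*The sample is narrower than the eligibility limits suggest.* Section 3 excludes regular exercisers, patients whose movement is restricted by other disease and those needing continuous monitoring. Section 9 uses activity questionnaires to make the sample more alike, and recruitment is from the genitourinary clinic and the wards. The measure is joint range, and no document shows how strongly fitness drives it. These points argue for the lower end of the range. They do not deal with ECOG 0 to 2, ASA up to 3, extent of surgery or postoperative condition.

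*The trial is randomised.* That protects the comparison of arms, not a comparison by achieved level. A reader might also take the arm comparison to be fully secure, but excluding and replacing patients who cannot complete the walking can bias it too.

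**Conclusion.** The concern holds as a mismatch between a causal aim and non-randomised evidence, with nothing in the plan that adjusts for it or labels the result as associational. The direction is clear: if fitter patients both move more and recover sooner, achieved mobility will look beneficial whether or not it is.

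The size is not known. It rests on an assumed correlation that the documents do not supply and on which analysis is eventually run. At r = 0.3 the excess over 5% is modest (about 12% continuous, 9% binary); from r = 0.4 it is material (30% and 19%), and at r = 0.6 it dominates (92% and 71%). A change score escapes it only if fitness affects both measurements equally. This should be corrected before analysis. It does not affect the planned comparison of mobility between arms or the sample size.

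**What to change.** - **Sections 1 and 8.** Replace *needed* and *minimum required* with *level associated with*, and label the aim exploratory.
- **Section 16, adjustment.** Adjust any model of recovery or complications on mobility for a short set of variables known before surgery: baseline activity score (from the Section 9 questionnaires), ECOG, ASA and procedure class, each coded with few categories. State that this reduces confounding but does not remove it. Do not rely on adding arm for this purpose.
- **Section 16, few events.** Keep the set small. At an assumed 20% to 30% complication rate there are 80 × 0.2 = 16 to 80 × 0.3 = 24 events. With mobility and the four covariates at one term each, that is 16/5 = 3.2 to 24/5 = 4.8 events per term, so specify penalised estimation if complications are few.
- **Section 16, causal claims.** State that claims about cause rest only on the comparison of arms as randomised, with all randomised patients kept in it, and reconcile this with the exclusion and replacement rule in Section 9. That comparison speaks to the walking instruction, not to a threshold.

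**Cost.** Two phrases and a few sentences. The covariates are collected or known before surgery. The price is a weaker claim for objective 2 and slightly less precision from the added terms.

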2 BACKGROUND

Early mobilization is considered an important element of postoperative care, however, it remains unclear how to best implement this intervention in clinical practice. One of the first surgeons to describe the concept of early mobilization after surgery was [name], a gynecologist in Chicago, in 1899 (1). Despite the report by Ries, the practice of early postoperative mobilization was slow to gain favor in North America and patients were still commonly kept on strict bed rest for several weeks after surgery to minimize pain and ensure adequate healing of wounds (2). It was not until the 1940s that early mobilization became accepted among surgeons after a number of observational studies suggested that this practice was not harmful to patients. Within the last 20 years, there has been significant progress in perioperative care with the development of standardized enhanced recovery pathways (ERPs). ERPs combine many different elements of care in the preoperative, intraoperative and postoperative periods, and aim to reduce morbidity, decrease hospital duration of stay, and improve patients' recovery after surgery (6). ERPs are comprised of up to 25 different interventions in the perioperative period; however, the relative contribution of each of these elements to the overall recovery process remains unclear.

Guidelines for perioperative care from the Enhanced Recovery after Surgery Society give early mobilization a strong recommendation grade, despite a very low level of evidence supporting its use. There is little evidence in the literature regarding strategies to promote compliance to early mobilization, and significant differences in mobilization goals exist between programs.

The use of 3D motion tracking technology in clinical practice started in 2017(10). This technology uses wireless inertial measurement units which could be used in clinical settings to objectively measure movement patterns (the joint range of movement and the distance of movement) during functional activities. These data analyzed by the software and yield further calculation representing the bio-kinematics of body movement.

3 INCLUSION AND EXCLUSION CRITERIA

Inclusion Criteria

To be included in this study, participants must meet the following criteria:

1. Age \geq 18 years of age.
2. Ambulant inpatient with a stay of \geq 2 days after any oncologic surgery.
3. ECOG scale of performance status of less than 3.
4. American Society of Anesthesiologist score (ASA) 3 or less

PROTOCOL TITLE: Does increased mobility assessed with 3D motion tracking technology lead to early post-operative recovery among patients undergoing oncologic surgeries

5. Participants who do not engage in regular exercise regimen before the surgery (other than regular occupational physical therapy).
6. Participant or legal representative must understand the investigational nature of this study and sign an Independent Ethics Committee/Institutional Review Board approved written informed consent form prior to receiving any study related procedure.

Exclusion Criteria

Patients with altered mental status, psychiatric illness, ECOG scale performance status 3 or more, ASA score of 4, participants who engage in regular exercise regimen before surgery (at least one session per week), restricted movement due to other diseases or those who require continuous monitoring will be excluded from this study.

Inclusion of Women and Minorities

Women and members of all races and ethnic groups are eligible for this study. Pregnant women are eligible for this study.

4 LOCAL AND STUDY-WIDE NUMBER OF SUBJECTS

80 patients will be included in this study. All data will be identified and the duration of the study will be 24 months. Participant recruitment will occur through written informed consent prior the start of the study after thorough description.

5 LOCAL AND STUDY-WIDE RECRUITMENT METHODS

Subjects will be identified from the Roswell Park Comprehensive Cancer Center Genitourinary (GU) clinic and in the inpatient wards when they are scheduled for inpatient oncological surgical procedures. All clinic staff will be informed about the study to help with recognizing patients. When a potential patient is identified in clinic, one of the study team members will be notified and will discuss the study aims, risks and benefits. The subject will then be asked to sign an informed consent after proper review.

6 MULTI-SITE RESEARCH

N/A

7 STUDY TIMELINES

The study duration is 24 months or until target accrual is reached. Subjects will be on study until they are discharged from the hospital. Subjects will be followed 30 days post discharge to note any complications or readmission. A post study questionnaire will be given to participants during one of their follow up visits which happen 2 weeks, 6 weeks, 3 months post discharge or over the phone if missed.

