Sample Size Determination: The power calculations are based on the primary analysis, which compares the changes in measures of mobility between the two groups. Since the form of the models is unknown beforehand, a simplified and conservative power calculation is based on comparing the mean change (baseline to discharge) in a given mobility measure between groups using a two-sided, two-sample t-test. With a sample size of n=40 per group, we have 80% power (at $\alpha = 0.05$) to detect a difference of at least 0.63 standard deviations. Such a moderate effect size would be considered clinically relevant.

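### Complications are noted until 30 days after discharge with no fixed window from surgery, so time under observation depends on length of stay, which is itself an endpoint component

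*Combined protocol and SAP*

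**What the plan says.** Section 7 (Study Timelines) sets the follow-up: "Subjects will be followed 30 days post discharge to note any complications or readmission". Section 9 (Procedures Involved) agrees: "We will continue to follow them for 30 days post discharge to note any complications or readmission". In both, discharge starts the 30-day clock.

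Section 8 (Study Endpoints) includes in the primary endpoint "early discharge from the hospital and 30 days surgical related complications and readmissions". It does not say whether those 30 days run from surgery or from discharge. Discharge timing and complications are components of the same endpoint.

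Section 16 (Statistical Plan) handles complications as a secondary analysis: "The complication status (present/absent) and grades will be summarized by group and compared using Fisher's exact test or the chi-square test, as appropriate". It states no window and makes no allowance for differing observation time.

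Section 3 requires a postoperative stay of at least 2 days and sets no maximum. No section fixes a window counted from surgery. The gastrointestinal and chest symptoms in Section 9 are a separate set of outcomes, assessed "until they are discharged from the hospital"; they are not part of this point.

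**The concern.** A yes/no complication outcome has the same meaning in two arms only if patients are observed for the same time from the same origin. Here the end of observation is tied to discharge, which happens after randomization and which the trial hopes to bring forward. Randomization does not balance it.

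If more walking does shorten stay, intervention patients are observed for fewer days after surgery. Even with no effect on complications, that arm would then be expected to show slightly fewer. The lean would favour the trial's own hypothesis. Two analysts could also classify the same event differently: a complication on postoperative day 35 in a patient who stayed 7 days falls inside a discharge-based window (7 + 30 = 37 days) and outside a surgery-based one.

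**Working it through.** **The plan's own figure.** Section 16 gives 80% power with 40 per group for a difference of 0.63 SD in mobility change, "using a two-sided, two-sample t-test". The normal approximation gives Φ(0.63 × √(40/2) − 1.96) = Φ(0.857) = 80.4%. The exact noncentral t calculation gives 79.5%, with 0.634 SD detectable at 80% power. The figure reproduces. It rests on mobility and does not involve complications, so nothing below changes it.

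**Observation time.** Under Sections 7 and 9, the window from surgery is stay + 30 days.

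| Stay (days) | Window from surgery (days) | Relative to 30 days |
|---|---|---|
| 2 (minimum, Section 3) | 32 | +7% |
| 5 | 35 | +17% |
| 7 | 37 | +23% |
| 10 | 40 | +33% |
| 14 | 44 | +47% |

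Only the 2-day minimum comes from the documents. The other stays, and every risk below, are assumptions.

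**Simple estimate.** Artificial difference = difference in mean stay × daily risk late in follow-up. With a 1-day difference and 0.1% to 0.5% per day, this is 0.1 to 0.5 percentage points, or 40 × 0.001 = 0.04 to 40 × 0.005 = 0.2 events per arm.

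**Constant hazard, equal in both arms.** With p the 30-day risk and L the mean stay, risk over the window = 1 − (1 − p)^((30 + L)/30). For p = 30%, stays of 7 and 5 days give 1 − 0.70^(37/30) = 35.6% and 1 − 0.70^(35/30) = 34.0%.

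| Stays compared (days) | p = 10% | p = 30% | p = 50% |
|---|---|---|---|
| 5 vs 4 | 0.3 points | 0.8 | 1.0 |
| 7 vs 5 | 0.6 | 1.55 | 2.0 |
| 10 vs 5 | 1.5 | 3.8 | 4.9 |
| 14 vs 7 | 2.1 | 5.1 | 6.4 |

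**Lower risk after day 30.** A constant hazard is likely to overstate the effect if complications cluster early. Let the hazard after day 30 be a fraction f of the 30-day average h = −ln(1 − p)/30, which is 0.0119 per day at p = 30%. Risk = 1 − (1 − p) × exp(−f × h × L). For 7 vs 5 days:

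- f = 0.10: 30.6% vs 30.4%, a difference of 0.2 points
- f = 0.25: 31.4% vs 31.0%, a difference of 0.4 points
- f = 0.50: 32.9% vs 32.0%, a difference of 0.8 points

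**Effect on the test.** With 40 per arm, p = 30%, a constant hazard and no true effect, the two-sided rejection rates at the 5% level are:

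| Stays (days) | Chi-square (uncorrected) | Fisher's exact |
|---|---|---|
| 5 vs 5 | 4.8% | 2.8% |
| 7 vs 5 | 5.1% | 3.0% |
| 14 vs 7 | 7.7% | 4.8% |

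**After the fix.** With a window of day 0 to day 30, every patient contributes 30 days and the part of the difference caused by stay is zero.

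**The case against.** **A contradiction between sections.** A reader might infer that Section 8 promises complications within 30 days of surgery while Sections 7 and 9 deliver something else. The text does not support this. In Section 8 the reference to surgery describes the kind of complication and does not start the clock. The same 30 days also covers readmission, which is naturally counted from discharge. Read that way, the three sections agree. Nor does the plan promise a rate counted from surgery that it then fails to report.

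**Follow-up is not an analysis window.** Sections 7 and 9 say how long events are noted, not which events enter the comparison. If the sponsor meant 30 days from surgery, follow-up merely runs longer than needed and there is no lean. This is fair, and it makes the concern conditional. It does not remove it: Section 16 offers no other window, so an analyst following the text would count everything noted.

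**Size.** A reader might also infer that the complication comparison is seriously biased. For a difference of a day or two in stay, the arithmetic says otherwise. The 14 vs 7 day case that does show an effect has no support in the documents. Complications are also a secondary analysis in Section 16.

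**A trade-off.** Counting from discharge gives every patient equal time at home, and a day-30 cut-off drops later events in long-stay patients. That is true. It argues for keeping discharge as the origin for readmission and for still listing late complications.

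**Conclusion.** The point holds as a minor one. The time origin for the 30 days in Section 8 is undefined, and the only operational window, in Sections 7 and 9, lengthens with hospital stay. The yes/no comparison in Section 16 therefore leans slightly toward whichever arm goes home sooner.

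The size is about 0.1 to 2 percentage points for a 1- to 2-day difference in stay, with almost no effect on type I error at 40 per arm. It would be larger only if stays differed greatly. These figures rest on assumed stays, assumed 30-day risks of 10% to 50% or a late risk of 0.1% to 0.5% per day, and equal hazards in the two arms. The documents supply none of these values and do not show that stay will differ between arms. The stated power is unaffected.

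**What to change.** In Sections 8 and 16, define the complication comparison as surgery to postoperative day 30 for every patient. Record the onset date of each complication; the documents do not say that this is already done. Count readmission to 30 days after discharge as a separate outcome, and list complications after postoperative day 30 descriptively. Sections 7 and 9 can keep their follow-up period, with a cross-reference to the definition.

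Discharge plus 30 days always reaches postoperative day 30, so no visits are added. The cost is a few sentences, one date field per complication, and leaving late events out of the main comparison. The sample size of 40 per arm and the power of about 80% stay as they are.
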